#### **10.2 ADVERSE EVENT CHARACTERISTICS**

**CTCAE term (AE description) and grade:** The descriptions and grading scales found in the revised NCI Common Terminology Criteria for Adverse Events (CTCAE) version 5.0 will be utilized for AE reporting. All appropriate treatment areas should have access to a copy of the CTCAE version 5.0. A copy of the CTCAE version 5.0 can be downloaded from the CTEP web site http://ctep.cancer.gov/protocolDevelopment/electronic applications/ctc.htm.

'Expectedness': AEs can be 'Unexpected' or 'Expected' for expedited reporting purposes only. Expected AEs are defined as those described in the Umbralisib Investigator Brochure.

#### Definitions of Adverse Events

An adverse event (AE) is any untoward medical occurrence in a patient or clinical investigation patient administered a pharmaceutical product. An AE does not necessarily have to have a causal relationship with this treatment. An adverse event (AE) can therefore be any unfavorable and unintended sign (including an abnormal laboratory finding, for example), symptom, or disease temporarily associated with the use of a medicinal product, whether or not considered related

to the medicinal product. This includes any occurrence that is new in onset or aggravated in severity or frequency from the baseline condition.

In clinical studies, an AE can include an undesirable medical condition occurring at any time, including run-in or washout periods, even if no study treatment has been administered. The NCI Common Terminology Criteria for Adverse Events (CTCAE) v4.0 is to be used for the grading of severity of symptoms and abnormal findings. For adverse events not covered by the NCI-CTCAE Version 4.0 grading system, the following definitions will be used:

- **Grade 1**: Mild; asymptomatic or mild symptoms; clinical or diagnostic observations only; intervention not indicated.
- **Grade 2:** Moderate; minimal, local or non-invasive intervention indicated.
- **Grade 3**: Severe or medically significant but not immediately lifethreatening; hospitalization or prolongation of hospitalization indicated.
- **Grade 4**: Life-threatening consequences; urgent intervention indicated.
- **Grade 5**: Death related to AE.

# 10.3 ADVERSE EVENTS (AES) AND TREATMENT EMERGENT ADVERSE EVENTS (TEAES)

All AEs and SAEs occurring on study will be listed by patient. Adverse events will be collected per the Moffitt SOP for adverse events, serious adverse events, and unanticipated problems. For the purpose of this trial, adverse event collection:

- Occurs after first dosing of study medication (Cycle 1, Day 1) and through the end of the study or up through 30 days after the last dose of study treatment, or
- Is considered treatment-related regardless of the start date of the event, or
- Is present before first dosing of study medication but worsens in intensity or the investigator subsequently considers treatment-related.

Adverse Events that are considered at least possibly related to study treatment will be tabulated as well as deaths, SAEs, and events resulting in treatment discontinuation.

#### 10.4 ADVERSE EVENTS/SERIOUS ADVERSE EVENT CAUSALITY ASSESSMENT

The Investigator must also assess the relationship of any adverse event to the use of study drugs (whether none, one, or both), based on available information, using the following guidelines:

- Not Related: Clear-cut temporal and/or mechanistic relation to a cause other than the study drug(s).
- **Doubtful**: There is no reasonable possibility that the event is related to the study drug(s) but a definite cause cannot be ascertained.
- **Possible**: There is still a reasonable possibility that the cause of the event was the study drug(s) but there exists a more likely cause of the event such as complications of progressive disease.
- **Probable**: The most likely cause of the event is the study drug(s) but other causes cannot be completely excluded.
- **Definite:** Clear cut temporal and/or mechanistic relation to the study drug(s). All other

causes have been eliminated. Events classified as definite will often be confirmed by documenting resolution on discontinuation of the study drug and recurrence upon resumption.

#### 10.4.1 RECORDING OF ADVERSE EVENTS

All adverse events of any patient during the course of the study will be recorded in the Moffitt On Core electronic database. The investigator will give his or her opinion as to the relationship of the adverse event to study drug treatment (i.e., whether the event is related or unrelated to study drug administration – umbralisib). If the adverse event is serious, it should be reported as described in Sections 10.5.2 and 10.6. Other untoward events occurring in the framework of a clinical study are also to be recorded as AEs (i.e., AEs that occur prior to assignment of study treatment that are related to a protocol-mandated intervention, including invasive procedures such as biopsies, medication washout, or no treatment run-in).

All AEs regardless of seriousness or relationship to umbralisib treatment spanning from Cycle 1, Day 1 until 30 calendar days (+/-7 days) after discontinuation or completion of protocol-specific treatment as defined by the protocol for that patient, are to be recorded.

## 10.4.1 ABNORMAL LABORATORY VALUES AND VITAL SIGNS

The reporting of abnormalities of vital signs as adverse events should be avoided. Abnormalities of vital signs should not be reported unless any criterion for an SAE is fulfilled, the vital signs abnormalities cause the patient to discontinue study treatment, or the investigator insists that the abnormality should be reported as an AE. Abnormal laboratory results should be recorded as an adverse event if they are associated with an overdose, require or prolong inpatient hospitalization, or are otherwise considered clinically significant by the investigator. If an abnormal laboratory value or vital sign is associated with clinical signs and/or symptoms, the sign or symptom should be recorded as an AE, and the associated laboratory value or vital sign should be considered additional information to record related to the AE. If the laboratory abnormality is a sign of a disease or syndrome, only the diagnosis needs to be recorded on the SAE Report Form or AE eCRF.

Clinical Laboratory Results will be summarized. Summary statistics for actual values and for changes from baseline will be tabulated for laboratory results by scheduled visit. Patients with laboratory values outside of the normal reference range at any post-baseline assessment will be summarized and graded per NCI CTCAE Version 5.0 when applicable. Patient incidence of abnormal laboratory results will be summarized by treatment group and maximum grade for each abnormal laboratory finding.

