## 3.1 INCLUSION CRITERIA

Patients must meet all of the following inclusion criteria to be eligible for participation in this study:

- 1) Have a diagnosis of B-cell CLL that has not been previously treated and now warrants treatment consistent with accepted iwCLL criteria (Hallek 2018) for initiation of therapy. Any one of the following conditions constitute CLL that warrants treatment:
  - a) Evidence of progressive marrow failure as manifested by the onset or worsening of anemia and/or thrombocytopenia, or
  - b) Massive (i.e., lower edge of spleen ≥ 6 cm below the left costal margin), progressive, or symptomatic splenomegaly, or
  - c) Massive (i.e., ≥ 10 cm in the longest diameter), progressive, or symptomatic lymphadenopathy, or
  - d) Progressive lymphocytosis in the absence of infection, with an increase in blood absolute lymphocyte count (ALC) >50% over a 2-month period or lymphocyte doubling time of <6 months (as long as initial ALC was  $\geq$  30,000/µL), or
  - e) Autoimmune anemia and/or thrombocytopenia that is poorly responsive to corticosteroids or other standard therapy, or
  - f) Symptomatic or functional extranodal involvement (e.g. skin, kidney, lung, or spine), or
  - g) Constitutional symptoms, defined as any one or more of the following diseaserelated symptoms or signs occurring in the absence of evidence of infection:
    - i) Unintentional weight loss of  $\geq 10\%$  within the previous 6 months, or
    - ii) Significant fatigue (≥ Grade 2), or
    - iii) Fevers >100.5°F or 38.0°C for  $\ge$ 2 weeks, or
    - iv) Night sweats for >1 month.
- 2) Adequate organ system function, defined as follows:
  - a) Absolute neutrophil count (ANC)  $\geq$  1,000/mm^3 platelet count  $\geq$  30,000/mm^3, (ANC  $\geq$  500/mm^3 and platelet count  $\geq$  20,000/mm^3 permitted if known marrow involvement). Growth factors are permitted at any time during the study, but not to meet eligibility criteria.
  - b) Total bilirubin ≤1.5 times the upper limit of normal (ULN) (unless diagnosed with Gilbert's syndrome).
  - c) Alanine aminotransferase (ALT) and aspartate aminotransferase (AST) ≤2.5 x ULN if no liver involvement or ≤5 x the ULN if known liver involvement
  - d) Calculated creatinine clearance >30 mL/min (as calculated by the Cockcroft-Gault or MDRD formula, 24 hour urine Cr clearance also acceptable)
- 3) ECOG performance status  $\leq 2$
- 4) Male or female  $\geq$  18 years of age

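### The laboratory abnormality table in Section 10.4.1 ignores baseline grade, so in this single-arm CLL trial it cannot separate disease at entry from change on umbralisib

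*Combined protocol and SAP*

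**What the plan says.** Two sections carry the number 10.4.1; the relevant one is Abnormal Laboratory Values and Vital Signs. It plans three laboratory outputs:

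- By-visit summaries: "Summary statistics for actual values and for changes from baseline will be tabulated for laboratory results by scheduled visit".
- A graded summary of out-of-range values: "Patients with laboratory values outside of the normal reference range at any post-baseline assessment will be summarized and graded per NCI CTCAE Version 5.0", qualified by a phrase limiting grading to tests where it applies.
- An incidence table: "Patient incidence of abnormal laboratory results will be summarized by treatment group and maximum grade for each abnormal laboratory finding". There is only one treatment group.

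Section 3.1 sets the entry conditions. Item 1 lists alternative reasons for needing treatment. Item 1a is "Evidence of progressive marrow failure as manifested by the onset or worsening of anemia and/or thrombocytopenia, or", and item 1d begins "Progressive lymphocytosis in the absence of infection, with an increase in blood absolute lymphocyte count". Item 2a asks for ANC of at least 1,000/mm³ and platelets of at least 30,000/mm³. Lower floors of 500 and 20,000 are "permitted if known marrow involvement".

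Adverse events have their own rule. One of the criteria in Section 10.3 is that the event "Is present before first dosing of study medication but worsens in intensity"; the same bullet also admits events later judged treatment-related. Section 10.8.5 records a pre-existing condition only if it worsens.

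**The concern.** The incidence table counts a state (out of range at some time after baseline), not a change. A patient who enters with low platelets and stays the same is counted, and so is one who improves without reaching the normal range. The maximum is taken over all later visits, and Section 5 schedules hematology and chemistry from Cycle 1 Day 8. A patient whose counts recover over three months is therefore still counted if the early draws were abnormal.

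In a randomized trial the control arm would show this background. Here the patient's own baseline is the only reference, and this table does not use it. Safety is a named secondary objective. A reader of the table could not tell how much of a hematology row is CLL at entry and how much arose or worsened on treatment.

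Other parts of the protocol do use baseline. Section 10.1 frames laboratory safety in terms of clinically significant changes. Section 8.5 describes on-drug lymphocytosis as a rise of at least 50% from baseline to a count above 5,000/mcL. Section 6.3 separates disease-related cytopenias from drug-related ones for dose modification.

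**Working it through.** The documents give no figure for this table, so there is nothing to reproduce. The check has two parts.

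**1. Does any other text supply the missing condition?**

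- Section 9.2 adds descriptive statistics (mean, SD, median, range, percentiles) and data listings. It has no grade shift.
- Sections 10.2 (adverse event definition), 10.3 and 10.8.5 refer to baseline, but for adverse events.
- Section 10.8.2 says when a laboratory result becomes an adverse event. It does not govern the laboratory table.
- Section 6.3 concerns dose modification.

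None attaches a baseline-grade condition to the table, and no shift table appears anywhere. Section 10.4.1 also does not say whether the screening or the Cycle 1 Day 1 draw is the baseline.

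**2. How large can the background be?** For a single laboratory test, let

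- N = number of patients: 35 (about the number expected for analysis, Section 9.1) or 40 (the enrollment ceiling there, relevant because the safety population is all treated patients);
- b = share out of range at baseline: not in the documents, assumed 10% to 70%;
- s = share of those still out of range at one or more post-baseline draws: assumed 1, with 0.8 as a check;
- e = rate of new abnormality in the rest: assumed.

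Expected table count = N × [b·s + (1 − b·s)·e].

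No drug effect (e = 0), s = 1:

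- N = 35: 35 × 0.10 = 3.5, up to 35 × 0.70 = 24.5.
- N = 40: 40 × 0.10 = 4, up to 40 × 0.70 = 28.

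With s = 0.8 and N = 35: 35 × 0.08 = 2.8, up to 35 × 0.56 = 19.6.

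How the table responds to case mix and to new abnormalities (N = 35, s = 1):

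- b = 30%, e = 5%: 35 × (0.30 + 0.70 × 0.05) = 11.7 counted, of whom 35 × 0.70 × 0.05 = 1.2 are new.
- b = 30%, e = 20%: 35 × (0.30 + 0.70 × 0.20) = 15.4 counted, of whom 35 × 0.70 × 0.20 = 4.9 are new.
- b = 10%, e = 5%: 35 × (0.10 + 0.90 × 0.05) = 5.1 counted.
- b = 70%, e = 5%: 35 × (0.70 + 0.30 × 0.05) = 25.0 counted.

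At b = 30%, a fourfold rise in e moves the table only from 11.7 to 15.4. With e held at 5%, moving b across its assumed range takes the count from 5.1 to 25.0. Within these assumptions the table tracks who was enrolled more than what happened on drug. Patients abnormal at baseline whose grade then rises are not modelled; they would add to the emergent counts.

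**The case against.** The strongest reply is that this is one descriptive table and that the plan does not ignore baseline. Section 9.2 provides medians, ranges and percentiles as well as means, Section 10.4.1 applies summary statistics to changes from baseline at each visit, and the listings hold every value. A reader could rebuild grade shifts from them. That softens the problem. It does not remove it, because group summaries of values do not show how many patients rose in grade, and a listing is not a planned analysis.

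It is also fair that the entry criteria do not guarantee abnormal counts. Items 1a to 1g are alternatives, some patients will qualify on nodes, spleen or symptoms alone, and the lowest count floors are an exception. This is why the prevalence is left as a wide range.

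Three stronger readings are tempting, and the documents do not support them:

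- A reader might infer that the trial's hematologic toxicity could not be set against the phase 1 figures in Section 1.2.2.1 (neutropenia 13%, anemia 9%, thrombocytopenia 7%). Those are Grade 3 or 4 adverse event rates. Their counterpart here is the adverse event tabulation, which follows other rules, so they are not a like-for-like comparator for this table.
- A reader might infer that adverse event rates or stopping decisions are inflated. A laboratory result becomes an adverse event on grounds such as clinical significance, and Section 6.6 acts on treatment discontinuations and drug-attributed deaths. Neither uses this table.
- A reader might want a worsening-only count to replace the table. A patient already at Grade 4 has no higher laboratory grade to reach, so a further fall would disappear. If platelets below 25,000/mm³ are Grade 4 (a CTCAE limit assumed here, not printed in the documents), a patient admitted at 20,000 to 24,999 would be in that position.

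**Conclusion.** The point holds for the laboratory incidence table and goes no further. As written, the table mixes abnormality present at entry with abnormality arising or worsening on treatment, and no other section repairs it. With no drug effect it would still count 3.5 to 24.5 of 35 patients on a given test (4 to 28 of 40), assuming 10% to 70% were out of range at baseline and remained so for at least one later draw. The width of that range reflects the absence of a prevalence in the documents; the fault in the counting rule does not depend on where in it the truth lies. The overall response rate test, the adverse event tables and the stopping rules are unaffected. This is a worthwhile, inexpensive improvement to safety reporting, not a threat to the trial's conclusions on efficacy.

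**What to change.** Keep the existing table and add to Section 10.4.1:

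- a definition of baseline as the last value before the first dose, which settles the choice between the screening and Cycle 1 Day 1 draws;
- baseline-to-worst CTCAE grade shift tables for hemoglobin, ANC, platelets, lymphocytes, ALT, AST, bilirubin and creatinine;
- incidence of treatment-emergent laboratory abnormalities, defined as a rise of at least one grade from baseline, by worst post-baseline grade;
- a separate baseline row for patients already at Grade 4, with their change in actual values.

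All eight tests are on the local laboratory lists in Section 5.1.1, and hematology and chemistry are drawn at screening, Cycle 1 Day 1 and later visits, so no new sampling is needed. The cost is some SAP text and a little more programming. The one limitation, that patients at Grade 4 at baseline cannot rise a grade, is handled by the separate row and by keeping the original table alongside.

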## 10.4.2 HANDLING OF ADVERSE EVENTS

All adverse events resulting in discontinuation from the study should be followed until resolution or stabilization. Patients should be followed for AEs for 30 calendar days (+/-7 days) after

discontinuation or completion of protocol-specific treatment (umbralisib). All new AEs occurring during this period must be recorded and followed until resolution unless, in the opinion of the investigator, these values are not likely to improve because of the underlying disease. In this case, the investigators must record his or her reasoning for this decision in the patient's medical record]. After 30 days, only AEs, SAEs, or deaths assessed by the investigator as treatment related are to be reported.

## 10.5 SERIOUS ADVERSE EVENTS

#### 10.5.1 DEFINITIONS OF SERIOUS ADVERSE EVENTS

The definitions of serious adverse events (SAEs) are given below. The investigator is responsible for ensuring that all staff involved in the study are familiar with the content of this section.

An SAE or reaction is defined as any untoward medical occurrence that:

- results in death, is immediately life-threatening,
- requires at least a 24-hour in-patient hospitalization or prolongation of existing hospitalization,
- results in persistent or significant disability/incapacity, and/or
- causes a congenital anomaly/birth defect.

Medical and scientific judgment should be exercised in deciding whether expedited reporting is appropriate in other situations, such as important medical events that may not be immediately life- threatening or result in death or hospitalization, but may jeopardize the patient or may require intervention to prevent one of the other outcomes listed in the previous definition. These should also usually be considered serious. Examples of such events are intensive treatment in an emergency room or at home for allergic bronchospasm; blood dyscrasias or convulsions that do not result in hospitalization; or development of drug dependency or drug abuse.

Progression of malignancy (including fatal outcomes), if documented by use of appropriate method (for example, as per iwCLL Hallek et al. 2018), should not be reported as a serious adverse event.

A suspected unexpected serious adverse reaction (SUSAR) is defined as an SAE that is suspected to be at least possibly related to study medication and is an unexpected event. SUSAR reporting is encompassed within SAE reporting guidelines as defined in this section.

Treatment within or admission to the following facilities is not considered to meet the criteria of "in-patient hospitalization" (although if any other SAE criteria are met, the event must still be treated as an SAE and immediately reported):

- Emergency Department or Emergency Room
- Outpatient or same-day surgery units
- Observation or short-stay unit
- Rehabilitation facility

- Hospice or skilled nursing facility, Nursing homes, Custodial care or Respite care facility
- Hospitalization during the study for a pre-planned surgical or medical procedure (one which was planned prior to entry in the study), does not require reporting as a serious adverse event.

It is important to distinguish between "serious" and "severe" adverse events, as the terms are not synonymous. Severity is a measure of intensity; however, an AE of severe intensity need not necessarily be considered serious. For example, nausea which persists for several hours may be considered severe nausea but may not be considered an SAE. On the other hand, a stroke which results in only a limited degree of disability may be considered only a mild stroke, but would be considered an SAE. Severity and seriousness should be independently assessed when recording AEs and SAEs.

Adverse events classified by the treating investigator as **serious** require expeditious handling and reporting to TG Therapeutics in order to comply with regulatory requirements. Serious adverse events may occur at any time from signing of the consent form through the 30-day followup period after the last study treatment. TG Therapeutics should be notified of all SAEs, regardless of causality, within 24 hours of the first knowledge of the event by the treating physician or research personnel. Report SAEs to TG Therapeutics at [contact] (copy [name][contact] and [contact] on an SAE Form (MedWatch FORM FDA 3500 or equivalent). Include the TG Therapeutics, Inc. tracking number (TGR-NTG-006) on the SAE report .SAEs are to be followed until resolution (with autopsy report, if applicable).

CLL progression or death due to CLL progression should be reported by the investigator as a serious adverse event only if it is assessed that umbralisib caused or contributed to the CLL progression (i.e. by a means other than lack of effect).

The investigator must review and sign off on the SAE data on the SAE report.

Transmission of the SAE report should be confirmed by the site personnel submitting the report.

Follow-up information for SAEs and information on non-serious AEs that become serious should also be reported to TG Therapeutics as soon as it is available; these reports should be submitted using the appropriate SAE form.

#### 10.6 SAE REPORTING REQUIREMENTS BY INVESTIGATOR TO FDA AND IRB

The investigator is responsible for reporting SAEs to the FDA in accordance with ICH guidelines, FDA regulations, and/or local regulatory requirements.

The investigator is responsible for reporting unexpected fatal or life-threatening events associated with the use of the study drugs to the FDA within 7 calendar days of the first knowledge of the event by the treating physician or research personnel. The investigator will report all related but unexpected SAEs including non-death/non-life-threatening related but unexpected SAEs (SUSAR) associated with the use of the study medications to the FDA by a written safety report within 15 calendar days of the first knowledge of the event by the treating physician or research personnel.

Investigators must report SAEs, SUSARs and follow-up information to their responsible Institutional Review Board (IRBs)/Independent Ethics Committee according to the policies of the responsible IRB (Research Ethics Committee).

